5.3 Inclusion of Vulnerable Subjects

Certain subjects are categorized as vulnerable populations and require special treatment with respect to safeguards of their well-being. For this clinical trial, examples include cognitively impaired or mentally disabled persons and intubated individuals who are sedated. When it is determined that a potential research subject is cognitively impaired, federal and institutional regulations permit researchers to obtain consent from a legally authorized representative (LAR). The study team will obtain consent from these vulnerable subjects using an IRB-approved protocol-specific process for consent using a LAR. For subjects for whom a LAR gives consent, if the subject regains the capacity to consent during the course of the study, informed consent must be obtained from the subject and the subject offered the ability to leave the study if desired.

For this clinical trial, we will not enroll prisoners or detainees as subjects.

5.4 Lifestyle Considerations

During this study, subjects are asked to:

- Avoid getting pregnant during the study from Day 1 through Day 29.
- Not participate in the following types of trials for the treatment of COVID-19 or SARS-CoV-2 infection:

- Blinded or unblinded interventional trials that evaluate if a non-approved medication or intervention is effective are prohibited.
- Any other blinded interventional trials for treating COVID-19 are prohibited.
- If a subject is co-enrolled in a prohibited study noted above, this should be reported as a protocol deviation, but the subject should not be withdrawn from this trial to participate in the other study. Full follow-up should occur per protocol.
- Participation in both ACTT and these studies can only occur if the recommended blood collection volumes are not exceeded.
 - Co-enrollment in non-blinded (open-label) interventional studies that evaluate how to apply a standard of care intervention or strategy for patients with COVID-19 (e.g., comparing dose, duration or schedule of VTE prophylaxis regimens; ICU strategies such as proning, etc.) is permitted.
 - Co-enrollment in natural history studies of COVID-19 and/or studies of SARS-CoV-2 diagnostics is permitted.

5.5 Screen Failures

Following consent, after the screening evaluations have been completed, the investigator or designee is to review the inclusion/exclusion criteria and determine the subject's eligibility for the study. If there is any uncertainty, the PI should make the decision on whether a potential subject is eligible for study enrollment.

Only basic demographic information and the reason(s) for ineligibility will be collected on screen failures. Subjects who are found to be ineligible will be told the reason(s) for ineligibility.

Individuals who do not meet the criteria for participation in this study (screen failure) because of an abnormal clinical laboratory finding may be rescreened once.

5.6 Strategies for Recruitment and Retention

5.6.1 Recruitment

It is anticipated that patients with COVID-19 will present for hospitalization to participating clinical trial sites, and that no external recruitment efforts towards potential subjects are needed. Recruitment efforts may also include dissemination of information about this trial to other medical professionals / hospitals. The IRB will approve the recruitment process and all materials provided prior to any recruitment to prospective subjects directly.

Recruitment activities will include pre-screening activities and will begin with a brief discussion between study staff and the subject/LAR before consent. Some subjects will be excluded based on demographic data and medical history alone (e.g., pregnant, < 18 years of age, on hemodialysis, etc.). In addition, information about the study will be presented to potential subjects or LAR and questions will be asked to determine potential eligibility after which time informed consent is obtained and further screening is completed (see Section 8.1.1).

5.6.2 Retention

Retention of subjects is critical to the success of the trial since the primary endpoint is measured at Day 29 (+ 6-day window) and every effort should be made to retain subjects in the study. As such, after hospital discharge, subjects will be reminded of subsequent study visits and every effort will be made to accommodate the subject's schedule to facilitate follow-up within the specified visit window. To facilitate retention, follow-up visits may be conducted by phone, home visit or remote telehealth procedure as per institutional standards if in-person visits at the clinical site on Days 15 and 29 are not feasible. The Day 22 visits are by phone call or remote telehealth procedure.

However, there are many circumstances that impact a site's ability to obtain outcome information after discharge. For example, given the clinical course of COVID-19, a subject may be readmitted to another hospital after discharge and therefore be unavailable at Day 15 or Day 22. Even if a study visit is missed, every effort should be made to keep subjects in the study to monitor for safety, readmission and mortality. Subjects should not be withdrawn from the study because a site is unable to contact them for a follow-up visit.

Subjects should not be withdrawn from this trial due to terminal illness. If a subject or family is pursuing hospice or withdrawal of care, the study visits can be curtailed as needed, but these subjects (or their LARs) should be encouraged to remain in study for the Day 29 endpoint evaluation by chart review or phone call.

In addition, in ACTT-4 we will have a visit two months after randomization to assess long term efficacy and safety outcomes. This visit will be conducted by phone or remote telehealth procedure. Because of this visit, sites will need to plan for how they will contact subjects at this late time point.

5.6.3 Compensation Plan for Subjects

Compensation, if any, will be determined locally and in accordance with local IRB requirements, and subject to local IRB approval.

5.6.4 Costs

There is no cost to subjects for the research tests, procedures/evaluations and study product while taking part in this trial. Procedures and treatment for clinical care including costs associated with hospital stay may be billed to the subject, subject's insurance or third party.

6. STUDY PRODUCT

6.1 Study Product(s) and Administration

Subjects will be randomized into one of two arms (1:1).

| Arm 1 | Arm 2 |
|---------------------------------------|---|
| Baricitinib tablets + Placebo IV + | Placebo tablets + Dexamethasone IV + |

| | |
|---------------|---------------|
| Remdesivir IV | Remdesivir IV |
|---------------|---------------|

6.1.1 Study Product Description

Remdesivir Component

Remdesivir is a single diastereomer monophosphoramidate prodrug designed for the intracellular delivery of a modified adenine nucleoside analog GS-441524. In addition to the active ingredient, the lyophilized and solution formulations of remdesivir contain the following inactive ingredients: water for injection, betadex sulfobutyl ether sodium, and hydrochloric acid and/or sodium hydroxide.

Baricitinib Component

Baricitinib is a Janus kinase (JAK) inhibitor with the chemical name [1-(ethylsulfonyl)-3-(4-(7H-pyrrolo(2,3-*d*)pyrimidin-4-yl)-1*H*-pyrazol-1-yl)azetidin-3-yl] acetonitrile and will be supplied in 36 count bottles. The treatment will be allocated as one bottle per subject, with some overage per bottle. Each tablet contains 2 mg of baricitinib and the following inactive ingredients: croscarmellose sodium, magnesium stearate, mannitol, microcrystalline cellulose, ferric oxide, lecithin (soya), polyethylene glycol, polyvinyl alcohol, talc and titanium dioxide.

Oral Placebo Component (Baricitinib)

Placebo for baricitinib tablets also manufactured by Eli Lilly and Company USA, and they contain lactose monohydrate, microcrystalline cellulose, croscarmellose sodium, and magnesium stearate. The coating for the placebo tablet is identical to that of the corresponding active tablet listed above. However, there is no lactose monohydrate in baricitinib, the active oral product.

Dexamethasone Component

Dexamethasone Sodium Phosphate Injection, USP, is an adrenocortical steroid anti-inflammatory drug. It is a water-soluble inorganic ester of dexamethasone. Each mL contains dexamethasone sodium phosphate equivalent to dexamethasone phosphate 4 mg or dexamethasone 3.33 mg; benzyl alcohol 10 mg added as preservative; sodium citrate dihydrate 11 mg; sodium sulfite 1 mg as an antioxidant; Water for Injection q.s. Citric acid and/or sodium hydroxide may have been added for pH adjustment (7.0 to 8.5). Dexamethasone is supplied as a 5 mL multi-dose vial.

Placebo Component (Dexamethasone)

The dexamethasone placebo will be 0.9 % sodium chloride injection, USP. The USP grade 0.9% Sodium Chloride Injection, or normal saline, is a sterile, nonpyrogenic, isotonic solution; each mL contains sodium chloride 9 mg. It contains no bacteriostatic agent, antimicrobial agent, preservatives, or added buffer and is supplied only in single-dose containers. The solution may contain hydrochloric acid and/or sodium hydroxide for pH adjustment (pH 5.3, range 4.5-7.0). This product will be used as the placebo for dexamethasone IV push administration at an equal volume at the same schedule.

6.1.2 Dosing and Administration

Dosing of the medications does not need to occur at the same time. Study Day 1 is the first day any of the 3 study products is administered (i.e., study remdesivir, baricitinib/po placebo, or dexamethasone/IV placebo given on study) and is used to determine timing of protocol assessments and safety analyses as outlined in SOA. Sites have 24 hours between randomization (enrollment) and initial study product administration.

Remdesivir

- Up to four doses of remdesivir are allowed prior to randomization. Remdesivir should be given as soon as possible after randomization. If a patient receives remdesivir in the emergency department late at night or early in the morning on day of enrollment, the dosing may be transitioned to daytime hours if desired by allowing a minimum 12-hour window between the pre-study dose and Day 1 dose.
- After Day 1, remdesivir should be given approximately every 24 hours +/- 2 hours. Protocol deviations do not need to be submitted if remdesivir given outside of this window. Protocol deviations should be submitted if a daily dose is missed completely.
- This dosing should occur as described regardless of the options for anti-inflammatory dosing discussed below.
- All subjects will receive remdesivir as a 200 mg intravenous (IV) loading dose on Day 1, followed by a 100 mg once-daily IV maintenance dose for the duration of the hospitalization up to a 10-day total course. If subjects already received the loading dose prior to study enrollment, then start at 100 mg/day on Day 1. Any doses of remdesivir given prior to enrollment will be counted, so the total duration of remdesivir (i.e. pre-enrollment + on this trial) is 10 days (i.e., a maximum of 10 total infusions). Any doses of remdesivir were administered prior to study enrollment should be documented in Advantage eClinical as a concomitant medication given prior to Day 1. The duration of dosing may be adjusted by the site similar to what is described in the package insert and based on a subject's clinical course and ultimate disease severity.

ANTI-INFLAMMATORY AGENTS (DEXAMETHASONE/IV PLACEBO + BARICITINIB/ PO PLACEBO)

- The anti-inflammatory agents should be given as soon as possible after randomization, but they also should be given around the same time so one arm is not receiving treatment sooner than the other arm.

For patients, who have received dexamethasone before enrollment as part of their clinical care:

- If a patient has received dexamethasone the day prior to enrollment, then the baricitinib/po placebo and dexamethasone/IV placebo can be administered right after randomization and this becomes Day 1.
- If a patient has received dexamethasone at any time on the day of enrollment but before randomization/enrollment, then there are several options as described below.
 - It is preferred to randomize and give remdesivir + dexamethasone/po placebo + baricitinib/IV placebo on the same calendar day as randomization. This could result in subjects receiving two doses of dexamethasone on Day 1 (a pre-study dose and an on-study dose of dexamethasone/IV placebo).

- If the site is concerned with this high dose of dexamethasone, sites have 24 hours between randomization (enrollment) and initial study product administration (i.e. both drugs may be delayed until the calendar day after randomization but within 24 hours of randomization).
- Alternatively, if necessary (but not preferred), sites may randomize and give remdesivir and baricitinib/po placebo on the same calendar day as randomization (this becomes Day 1) and on Day 2, give all other study products and submit a protocol deviation for missed dose of IV push study product on Day 1 and this missed dose of dexamethasone/IV placebo will not be made-up during the study. The subject will receive only 9 doses of dexamethasone/IV placebo from Day 2 through Day 10. This option allows the PI to decide the risk /benefit ratio of a potential double dose of dexamethasone on Day 1 for their patients.

For the baricitinib component, subjects will receive either active product or placebo as follows:

- Baricitinib will be administered as a 4 mg orally (po) (two, 2mg tablets) or dissolved for NG tube, daily for the duration of the hospitalization up to a 14-day total course.
- A placebo will be given as two tablets po or dissolved for NG tube, daily for the duration of the hospitalization up to a 14-day total course.
- See [Section 6.1.4](#) for dosing modifications for baricitinib for renal failure.
- See MOP for instructions on how to prepare and administer baricitinib to patients having difficulty swallowing

For dexamethasone component, subjects will receive either active product or placebo as follows:

- Dexamethasone will be administered as a 6 mg slow IV push over 3 to 5 minutes daily for the duration of the hospitalization up to a 10-day total course.
- A placebo will be given as an equal volume normal saline, as a slow IV push daily for the duration of the hospitalization up to a 10-day total course.
- If local standards use other means of administration (such as IV infusion), these may be used for both active and placebo after approval of the sponsor. Reports of intense perineal pain and/or burning are reported immediately after given IV push too quickly.
- Any pre-study dexamethasone (see exclusion criteria) is not counted towards the 10 day course.

Duration of therapy:

- IV remdesivir – up to 10 days while hospitalized (i.e., maximum of 10 total infusions pre-enrollment and during study).
- Oral baricitinib (or oral placebo) – 14 days while hospitalized (i.e., maximum of 14 total doses).
- IV dexamethasone (or IV placebo) – 10 days while hospitalized (i.e., maximum of 10 total doses).
- All medications stop on discharge from hospital.
 - Of note, if a subject is retained in the hospital for non-COVID-19 related issues and no longer requires supplemental oxygen and ongoing medical care (i.e., ordinal scale category 3), the PI may decide to discontinue all medications.

- If readmitted after discharge, see [Section 7.4](#).

6.1.3 Dose Escalation

Not Applicable

6.1.4 Dose Modifications

The protocol-required safety laboratories (per the SOA) are anticipated to be sufficient for evaluating for dose modifications, but if other laboratory data obtained as part of standard care are available, these should also be used in the evaluation.

Remdesivir component:

The infusion should be held and not given if the subject is found to have any of the following laboratory values:

- eGFR decreases to < 15 mL/min
 - Remdesivir infusion will resume when the eGFR increases to ≥ 15 mL/min and the potential benefit of giving remdesivir outweighs the potential risk.
 - If renal function worsens during the study to the point that they require hemodialysis or hemofiltration, remdesivir will be discontinued.
- ALT and/or AST increases to > 10 times upper limits of normal (ULN); resume remdesivir infusions when ALT and AST ≤ 5 times ULN.

Baricitinib/Oral Placebo component:

Dose of oral study product will be decreased or held based on eGFR. Specifically:

| eGFR Value | Dose of baricitinib or oral placebo |
|---|---|
| ≥ 60 mL/min | Two tablets (4 mg total) once daily No dose adjustment |
| 30 - < 60 mL/min | One tablet (2 mg) once daily |
| 15 - < 30 mL/min | One tablet (2 mg) QOD – every other day |
| < 15 mL/min or require hemodialysis or hemofiltration | Hold oral study product |

Oral study product should be temporarily interrupted if the subject develops any of the following during the study:

- eGFR decreases to < 15 mL/min; resume oral study product when eGFR ≥ 15 mL/min
- Absolute neutrophil count (ANC) < 500 cells/ μ L; resume oral study product when ANC ≥ 700 .
- Absolute lymphocyte count (ALC) < 200 cells/ μ L; resume oral study product when ALC ≥ 200 .
- ALT and/or AST increases to > 10 times ULN; resume oral study product when the ALT and AST ≤ 5 times ULN.
- New serious infection identified (i.e., SAE infection); may resume oral study product when PI believes that the infection is under control

Appendix D - ACTT-4: Baricitinib/Remdesivir vs Dexamethasone/Remdesivir

Any dose that is held as described above, may be given later that day if the laboratory parameters improve. Any daily dose that is missed during the study due to any reason is not made up. The treatment course continues as described above even if the subject becomes PCR negative while hospitalized. If oral study product is held for more than 2 days, consider that the subject may not be receiving any anti-inflammatory. If the clinical condition requires, an open-label (off-study) dexamethasone or other anti-inflammatory agent may be added while the oral study product is held. No protocol deviation for prohibitory medications (i.e., off-study dexamethasone) would be required for these days of anti-inflammatory coverage while the subject has oral study product held.

For laboratory values that meet permanent discontinuation thresholds (see [Section 7.1](#)), study product should be discontinued. However, if in the opinion of the investigator, the laboratory abnormality is due to intercurrent illness or another identified factor, laboratory tests may be repeated once.

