6.5.2 Prohibited Concomitant Therapy

As the study is comparing baricitinib to dexamethasone, additional baricitinib, dexamethasone and other glucocorticoids are prohibited unless the subject worsens and requires invasive mechanical ventilation (see Section 6.5.4). In addition, if oral study product is held for more than two days and the clinical condition requires, an open-label (off-study) dexamethasone or other anti-inflammatory agent may be added while the oral study product is held (Section 6.1.4). Exceptions to the steroid prohibition include: mineralocorticoids for standard indications are permitted (e.g., adrenal insufficiency, shock) and low-dose prednisone as part of immunosuppression regimen for solid organ-transplant patients is allowed (e.g., prednisone 5 mg po daily).

Strong inhibitors of organic anion transporter 3 (OAT3) such as probenecid are prohibited during the study.

Concomitant use of any other experimental treatment or off-label use of marketed medications intended as specific treatment for COVID-19 or SARS-CoV-2 infection, and not specified in the local or NIH COVID-19 Treatment Guidelines are prohibited. Specifically, use of any biologic therapy not specified on the written policy or guideline are prohibited including: monoclonal antibodies targeting cytokines (e.g., TNF inhibitors; interleukin-1[IL-1], IL-6 [tocilizumab or sarilumab]), or T-cells (e.g., abatacept); monoclonal antibodies targeting B-cells (e.g., rituximab, and including any targeting multiple cell lines including B-cells); JAK inhibitor(s) (e.g., baricitinib, imatinib, gefitinib, acalabrutinib, tofasitinib); and any type of interferon, convalescent plasma, or immunoglobulin (IgG) therapies for COVID-19. Similarly, the concomitant use of hydroxychloroquine to treat COVID-19 is prohibited unless it is included in the local institutional treatment guidelines (and even then, it is discouraged given the interaction with remdesivir).

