In ACTT-4, non-study product (off-study) baricitinib, dexamethasone and other glucocorticoids are prohibited unless the subject worsens to require invasive mechanical ventilation (ordinal score 7). Mineralocorticoids for standard indications are permitted (e.g., adrenal insufficiency, shock). Low-dose prednisone as part of immunosuppression regimen for solid organ-transplant patients is allowed as part of standard of care (e.g., prednisone 5 mg po daily).

If additional (off-study) baricitinib, dexamethasone or another glucocorticoid is given when a subject is not an ordinal scale category 7, the investigator should file a protocol deviation for use of the prohibited medication and decide whether the blinded study products should be discontinued. The subject should remain on study and continue with the SOA as described in the protocol though the Day 60 visit. An exception to this is when oral study product is held for more than 2 days and the clinical condition requires that an open-label (off-study) dexamethasone or other anti-inflammatory agent be added while the oral study product is held (see Section 6.1.4).

- The preference is to continue study medication as originally assigned (i.e. continue blinded baricitinib or placebo and continue blinded dexamethasone or placebo) as well as the remdesivir infusions. The subject should remain on study though the Day 60 visit.
- Recognizing the treating clinician may request to stop the randomized blinded study medication, the next preferred option is that the baricitinib/placebo po component and the dexamethasone/placebo IV component are discontinued without unblinding. This will allow the treating clinician to pick any regimen needed for the subject. In this scenario, remdesivir infusions should continue and the subject should remain on study though the Day 60 visit.
- If the treating clinician needs to know prior treatment, the site investigator can request that the subject treatment assignment be unblinded. This is the least preferred option as it unblinds treatment assignment. However, it is available to ensure clinicians have information available to give their patients optimal care. In this scenario, remdesivir infusions should continue and the subject should remain on study through the Day 60 visit.

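### ACTT-4 permits open-label dexamethasone during an oral-product hold without linking it to the blinded IV push, so a dexamethasone-arm subject can receive steroid twice

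*Protocol*

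**What the plan says.** All references are to Appendix D of the Protocol. Under 6.1, Arm 1 receives baricitinib tablets with IV placebo and Arm 2 receives placebo tablets with IV dexamethasone. Section 6.1.2 sets the push at 6 mg daily for "10 days while hospitalized (i.e., maximum of 10 total doses"), and 7.4 allows none after Day 10.

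Section 6.1.4 has hold rules for remdesivir and for the oral product, but none for the IV push. The oral triggers are eGFR below 15 mL/min, ANC below 500, ALC below 200, ALT or AST above 10 times ULN, and a fifth: "New serious infection identified (i.e., SAE infection); may resume oral study product when PI believes that the infection is under control". On missed doses it says: "Any daily dose that is missed during the study due to any reason is not made up".

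Once the oral hold exceeds 2 days, the site is told to "consider that the subject may not be receiving any anti-inflammatory". The permission follows: "If the clinical condition requires, an open-label (off-study) dexamethasone or other anti-inflammatory agent may be added while the oral study product is held". Then: "No protocol deviation for prohibitory medications (i.e., off-study dexamethasone) would be required for these days".

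Section 6.5.2 repeats the permission ("if oral study product is held for more than two days and the clinical condition requires") and does not mention the push. Section 6.5.4 sets the general rule for off-study steroid given outside ordinal category 7: the investigator files a deviation and must "decide whether the blinded study products should be discontinued". It then names the oral hold as an exception to that rule.

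**The concern.** The permission exists to fill a gap in anti-inflammatory cover. While the push is running, that gap exists in one arm only. The investigator is blinded and cannot tell which arm the subject is in, so acting on the permission as written can double the steroid in an Arm 2 subject who had no gap.

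What is at stake is subject safety. One of the hold triggers is a new serious infection, and 2.2.4.1 lists secondary infections among the common side effects of dexamethasone. The dose justification in 4.3.3 rests on the regimen tested in RECOVERY, which 2.1.1 gives as 6 mg once daily for up to 10 days. The appendix gives no support for a higher daily dose over several days.

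Section 6.1.2 shows that the authors recognised the issue elsewhere. For a possible double dose on Day 1 it describes the dose as high and gives concerned sites two ways to avoid it. Section 6.1.4 offers none for an overlap that can last longer.

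**Working it through.** **Who has lost cover when the oral product is held, up to Day 10**

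| | Tablets held | IV push continuing | Anti-inflammatory still given |
|---|---|---|---|
| Arm 1 | baricitinib | saline | none |
| Arm 2 | placebo | dexamethasone 6 mg/day | dexamethasone 6 mg/day |

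**Whether any section links open-label steroid to the push**

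- 6.1.4 and 6.5.2: no link.
- 6.5.4: the general rule would prompt a decision on the blinded products. The oral-hold exception can be read as removing that prompt, or as removing only the deviation report, which is all that 6.1.4 waives.
- 7.1.1: the investigator may stop study product for SAEs, severe laboratory abnormalities or other medical conditions. Starting open-label steroid is not named, and product stopped for a safety reason is not restarted.
- 7.1.1.2: both blinded products stop permanently for VTE, suspected drug-induced liver injury, new malignancy, confirmed systemic fungal infection or significant hypersensitivity. Open-label steroid is not on the list.
- 6.3.2.3: unblinding needs an SAE thought related to study drug. It does not reach laboratory holds that are not SAEs, or infections judged unrelated.

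**Size of the overlap**

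Inputs: 6 mg/day blinded dexamethasone and a maximum of 10 doses (6.1.2); last push on Day 10 (7.4); trigger of more than 2 days (6.1.4). The protocol sets no open-label dose, so 6 mg/day is assumed.

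Daily dose during overlap: 6 + 6 = 12 mg. Planned course: 10 × 6 = 60 mg.

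Let the hold start on Day d. If open-label steroid starts after three missed doses (Day d+3), overlap is 10 − (d+3) + 1 = 8 − d days. If it starts on the day of the third missed dose (Day d+2), overlap is 9 − d days. Both are maxima: they assume that the subject stays in hospital and that the oral hold, the push and the open-label steroid all continue to Day 10.

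| Hold starts | Maximum overlap (days) | Extra dexamethasone (mg) | Share of 60 mg |
|---|---|---|---|
| Day 2 | 6 to 7 | 36 to 42 | 60% to 70% |
| Day 3 | 5 to 6 | 30 to 36 | 50% to 60% |
| Day 5 | 3 to 4 | 18 to 24 | 30% to 40% |
| Day 7 | 1 to 2 | 6 to 12 | 10% to 20% |
| Day 8 | 0 to 1 | 0 to 6 | 0% to 10% |

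A hold from Day 9 or later gives no overlap. Day 2 is taken as the earliest start because the Day 1 laboratory results need not be reviewed before the first dose (1.2, notes to the Schedule of Assessments). Later scheduled safety laboratory days are 3, 5, 8 and 11; an infection hold can start on any day.

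The number of subjects affected cannot be derived. No hold rates are given, and Table 4 in 2.2.3.1 lists only terms reported in 5 or more subjects.

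**The case against.** The strongest reply is that the protocol already protects these subjects. Section 7.1.1 is broad enough to cover every oral-hold trigger, so an investigator who adds dexamethasone may stop the push without unblinding. Section 7.1.1.2 removes part of the liver and infection holds by stopping both blinded products. A new serious infection may well be judged related under 8.3.4.2, since it is a known risk of both drugs, and 6.3.2.3 then allows unblinding. The permission is also optional, depends on clinical need, and may be met with a non-steroid agent. The amendment history in section 10.4 of the main protocol shows that the clause was added on purpose. Finally, the protocol tolerates overlap elsewhere: 6.1.2 prefers same-day dosing on Day 1 despite a possible double dose, and 6.5.4 allows off-study steroid at category 7 while preferring that blinded products continue.

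Much of this stands. A reader might infer that the investigator has no way to stop the push, or that the protocol directs duplicate dosing. Neither is so: 7.1.1 gives the power, and the cover is discretionary.

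Two things survive. The 7.1.1 power is a stop that is not reversed, whereas the situation calls for a pause lasting as long as the oral hold. And nothing tells a blinded investigator to consider the push when open-label steroid starts; one reading of the 6.5.4 exception removes the only text that would.

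The objection is also right that the Day 2 figure stacks several maxima. For eGFR, ANC and ALC it would need an abrupt change after eligibility screening. ALT and AST are not among the ACTT-4 screening tests or exclusions, so a Day 2 liver hold is less remote, though still unusual. The MOP is not at hand and could add an instruction; 6.1.4 does not point to one.

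**Conclusion.** The point holds as a modest safety gap. Through Day 10, sections 6.1.4, 6.5.2 and 6.5.4 allow open-label dexamethasone on a rationale that is true only of Arm 1, and no section links it to the blinded push. An Arm 2 subject still on the push can therefore receive about 12 mg/day if the open-label dose is 6 mg, for at most 6 to 7 days in an extreme Day 2 hold and usually fewer.

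Three stronger inferences are not supported:

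- **Bias in the primary comparison.** The documents give no hold rates, the number affected is likely small, and no such effect is claimed.
- **The 60% to 70% excess as typical.** It is a ceiling for the earliest hold.
- **Demonstrated harm at 12 mg/day.** Section 6.1.5 calls reports of acute toxicity or death after glucocorticoid overdosage rare. The infection difference by steroid use in 2.2.3.1 (23% against 4.9%) compares non-randomised groups and is open to confounding.

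The case for change is that the duplication is unintended, invisible to the blinded investigator, and cheap to prevent.

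**What to change.** Add to 6.1.4: *If an open-label systemic glucocorticoid at a dose equivalent to dexamethasone 6 mg/day or more is started during an oral hold, temporarily hold the blinded IV push without unblinding while it is given; resume the push (not past Day 10, missed doses not made up) when it stops, at the latest when the oral product resumes.* In 6.5.4, limit the oral-hold exception to the deviation report.

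Under this rule Arm 1 misses only saline and Arm 2 keeps steroid cover at or above its assigned dose. The dose condition matters: pausing the push for a smaller open-label dose would under-treat Arm 2. The equivalents needed to apply it are already given with exclusion criterion 14 in 5.2. Stopping blinded product without unblinding is already an accepted option in 6.5.4.

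The cost is two wording edits. No new data are needed, because 6.5.3 already records corticosteroids through Day 29. The downside is that a few Arm 2 subjects receive open-label instead of blinded dexamethasone on those days. Open-label doses below the threshold would still add to the push, but by less than 6 mg/day.
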